## **12.2. Risk Minimization**

The potential risks associated with the ProGrip™ self-gripping polyester mesh were identified and have been successfully mitigated. Any potential risks associated with this study are further minimized by selecting qualified investigators and training study personnel on the CIP. Additionally, the study is performed per IFU indications and is on label use for the product.

In addition, investigators will be actively involved in the implantation and follow-up of the subjects implanted with ProGrip™ self-gripping polyester mesh.

Risks will be minimized by careful assessment of each subject prior to, during, and after implant of the ProGrip™ self-gripping polyester mesh. Prior to implant, it is recommended subjects undergo a complete physical evaluation.

Medtronic has further minimized the possibility of risks by performing required laboratory and pre-clinical testing prior to the POETRY study, implementing quality control measures into production processes, providing guidelines for subject selection and evaluation, and providing adequate instructions and labeling.

## 12.3.Potential Benefits

The information obtained from this study will be used to confirm the safety and efficacy of ProGrip™ self-gripping polyester mesh in abdominal suture line reinforcement. This information may lead to findings that could result in a reduction of adverse events for future subjects. The use of a preventative mesh could reduce the 10-50% rate of incisional hernias that occur after midline laparotomy and decrease complications associated with new surgery and incisional hernia repair. Additionally, information collected from this study may assist in the design of new product(s)/therapy(ies) and/or IFU.

## 12.4.Risk-Benefit Rationale

In use since 2008 for repair of inguinal and incisional hernia repair, numerous clinical trials have demonstrated the safety and effectiveness of ProGrip™ self-gripping polyester mesh (5-8). Including more than 2,400 patients in more than 20 clinical studies, ProGrip™ self-gripping polyester mesh demonstrates both a low global complication rate as well as a low device related complication rate (Publication summaries and data can be found in the ProGrip™ self-gripping polyester mesh Clinical Evaluation Report). Overall, a positive risk/benefit ratio has been demonstrated with ProGrip™ self-gripping polyester mesh as evidenced by these clinical studies, preclinical and biocompatibility testing. ProGrip™ self-gripping polyester mesh is a CE-Mark cleared device. Consequently, ProGrip™ self-gripping polyester mesh presents a favorable risk/benefit ratio to the subject. The instructions for use in addition to surgeon training, will instruct surgeons on proper use of the device to mitigate risk. There are currently no known interactions between ProGrip™ self-gripping polyester mesh and concurrent medical interventions.

## 13. Adverse Events and Device Deficiencies

Adverse event (AE) definitions used in this study are based on ISO 14155:2020 (Clinical Investigation of Medical Devices for Human Subjects -- Good Clinical Practice).

### 13.1.Adverse Events

AE definitions are provided in Section 13.4 (Table 4). During this study, only device and procedure related AEs, SAEs, DDs, and DDs with SADE potential will be collected throughout the study duration, starting at the time of signing the IC (this is a deviation from ISO 14155:2020).

Reporting of these events to Medtronic will occur on a paper AE Form. Each event must be reported separately. Documented pre-existing conditions are not considered AEs unless the nature or severity of the condition has worsened.

Anticipated Adverse Events following surgical procedures (primarily associated with anesthesia, listed in Table 4, need not be reported unless the adverse event worsens or is present outside the stated timeframe post-implant.

For AEs that require immediate reporting, initial reporting may be done by phone, fax, email or on the CRF completing as much information as possible. The completed AE CRF must be submitted to Medtronic as soon as possible.

Any medication/treatment associated with the treatment of an AE must be reported.

Subject deaths are also required to be reported. Refer to Section 13.8 for Subject Death collection and reporting requirements.

## **13.2.Device Deficiency**

The device deficiency (DD) definition is provided in Section 13.4 (Table 4). DD and DD with SADE potential information will be collected throughout the study and reported to Medtronic. Note that a DD that results in an AE to the subject should be captured as an AE only.

DD that did not lead to an AE but could have led to a SADE (i.e., if suitable action had not been taken, if intervention had not been made, or if the circumstances had been less fortunate) require immediate reporting.

## **13.3 Processing Updates and Resolution**

For any changes in status of a previously reported adverse event or DD (i.e. change in actions taken, change in outcome, change in relatedness), information needs to be updated on, or added to a new AE or DD paper form. All AEs must be followed until the AE has been resolved, is unresolved with no further actions planned, the subject dies or exits the study, or until study closure, whichever occurs first.

In the event that a subject is exited from the study prior to study completion, all efforts should be made to continue following the subject until all unresolved system or procedure related AEs, as classified by the investigator, are resolved, unresolved with no further actions planned, or 30 days, whichever occurs first.

At the time of study exit, all collected adverse events that are unresolved must be reviewed and an update must be reported.

## **13.4 Definitions/Classifications**

Where the definition indicates “device”, it refers to any device used in the study. This might be the device under investigation and includes but is not restricted to: ProGrip™ self-gripping polyester mesh.

**Table 4: Adverse Event and Device Deficiency Definitions**

General	
Adverse Event (AE)	
Untoward medical occurrence, unintended disease or injury, or untoward clinical signs (including abnormal laboratory findings) in subjects, users or other persons, whether or not related to the investigational medical device and whether anticipated or unanticipated
 
NOTE 1: This definition includes events related to the investigational medical device or the comparator.
 
NOTE 2: This definition includes events related to the procedures involved.
 
NOTE 3: For users or other persons, this definition is restricted to events related to investigational medical devices or comparators. (ISO 14155:2020, 3.2)

Adverse Device Effect (ADE)	
AE related to the use of an investigational medical device
 
NOTE 1: This definition includes AEs resulting from insufficient or inadequate instructions for use, deployment, implantation, installation, or operation, or any malfunction of the investigational medical device.
 
NOTE 2: This definition includes any event resulting from an error use or from intentional misuse of the investigational medical device.
 
NOTE 3: this includes 'comparator' if the comparator is a medical device. (ISO 14155:2020, 3.1)

Device Deficiency (DD)	
Inadequacy of a medical device with respect to its identity, quality, durability, reliability, usability, safety or performance.
 
NOTE 1: DD include malfunctions, use errors and inadequacy in the information supplied by the manufacturer including labeling.
 
NOTE2: This definition includes device deficiencies related to the investigational medical device or the comparator. (ISO 14155:2020, 3.19)

Relatedness	
Mesh Placement Procedure Related	An AE that occurs due to any procedure related to the implantation or surgical modification of the device.
Index Procedure Related	An AE that occurs due to the standard of care index surgical procedure
Device Related	An AE that results from the presence or performance (intended or otherwise) of the device.
Seriousness	
Serious Adverse Event (SAE)	
AE that led to any of the following
 
a) death,
 
b) serious deterioration in the health of the subject, users or other persons as defined by one or more of the following:
 
 
1) a life-threatening illness or injury, or
 
2) a permanent impairment of a body structure or a body function, including chronic disease, or
 
3) in-patient or prolonged hospitalization, or
 
4) medical or surgical intervention to prevent life-threatening illness or injury or permanent impairment to a body structure or a body function,
 
 
c) foetal distress, foetal death or a congenital abnormality or birth defect including physical or mental impairment
 
NOTE 1: Planned hospitalization for a pre-existing condition, or a procedure required by the CIP, without serious deterioration in health, is not considered an SAE.
 
(ISO 14155:2020, 3.45)

Serious Adverse Device Effect (SADE)	Adverse device effect that has resulted in any of the consequences characteristic of a serious adverse event.
	(ISO 14155:2020, 3.44)
Other	
Anticipated Adverse Event	
An AE inherent to a surgical procedure that is expected to occur in all subjects for a projected duration according to the Investigator's opinion, including, but not limited to:
 
 
▪ Postoperative transient nausea determined to be procedure related within the first 24 postoperative hours.
 
▪ Postoperative transient emesis determined to be
 

	
procedure related within the first 24 postoperative hours.
 

▪ Postoperative constipation determined to be procedure and/or medication related for the duration of medication administration for management of pain.

▪ Postop pain that the Investigator considers common and within normal limits for the procedure and is well-managed with medication.

Unanticipated Serious Adverse Device Effect (U(S)ADE)	
(Serious adverse) device effect which by its nature, incidence, severity or outcome has not been identified in the current risk assessment
 
NOTE 1: ASADE is an effect which by its nature, incidence, severity or outcome has been identified in the risk assessment.
 
(ISO 14155:2020, 3.51)

Serious Health Threat	
Signal from any adverse event or device deficiency that indicates an imminent risk of death or a serious deterioration in the health in subjects, users or other persons, and that requires prompt remedial action for other subjects, users or other persons
 
NOTE 1: This would include events that are of significant and unexpected nature such that they become alarming as a potential serious health hazard or possibility of multiple deaths occurring at short intervals.
 
(ISO 14155:2020, 3.46)

### **13.5 Reporting of Adverse Events**

The following events are generally considered reportable during the course of this study and should be reported to the sponsor:

- any DD,
- any procedure or device related AE or SAE,
- any Device Deficiency/Malfunction that might have led to an SADE if,
  - suitable action had not been taken or,
  - intervention had not been made or,
  - if circumstances had been less fortunate,
- new findings/updates in relation to already reported events.

Events will be reviewed by the sponsor to determine any reporting obligations to EC.

SAEs & Device Deficiencies/Malfunctions that might have led to an SADE need to be reported to the sponsor within 24 hours of becoming aware by completing an AE report form and sending it to Medtronic BOX [REDACTED]. When the AE report form is received by the sponsor, it will be marked as received and reviewed and saved in TMF. A deviation form is required if AE report form is not completed and AE was only reported via email to sponsor or if the event was reported outside of the required timeframe. Refer to Table 5 for reporting requirements of applicable events and device deficiencies.

**Table 5: Reporting requirements of applicable events and device deficiencies.**

Report	Responsible party	Submit to	Description / Time constraints
ADE, or DD	Investigator	Medtronic	Notify within 24h of notification of the event via data entry into Club Hernie database and AE form, telephone call and fax
	Medtronic	EC	Review within 48 hours per EC requirements
SAE, SADE, or Device Deficiency that might have led to a SADE	Investigator	Medtronic	Notify within 24h of notification of the event via data entry into Club Hernie database and AE form, telephone call and fax
	Medtronic	EC	Review within 48 hours per EC requirements Per EC requirements
U(S)ADE	Medtronic	IEC	Review within 48 hours per EC requirements Per EC requirements
	Medtronic or designee	Alternate applicable regulatory body	Report the results of an evaluation to EC and all participating investigators within 7 working days after Medtronic first receives notice of the effect, and 2 days if the U(S)ADE indicates an imminent risk of death, serious injury or serious illness and requires prompt remedial action.

Assessment of the occurrence of an AE will be based on changes in the subject's abbreviated physical examination, laboratory results and/or signs and symptoms. Adverse events will be monitored until a subject completes the study unless the Investigator determines the event is related to the device, in which case they will be monitored until resolution, if possible. Medical care will be provided, as defined in the informed consent, for any AE related to study participation. Adverse events will be collected on the Club Hernie database, and on an AE paper form to be sent to the sponsor and applicable source documentation. AE data will include but is not limited to; date of the AE, treatment, resolution, assessment of both seriousness and relationship to the investigational medical device. To the extent possible, the event to be recorded and reported is the event diagnosis as opposed to event symptoms (e.g., fever, chills, nausea and vomiting in the presence of a clinically diagnosed infection is to be reported as infection only). AEs occurring at procedure and up to and including 24 months follow-up will be recorded.

The following should not be considered an AE:

- A condition requiring a preplanned procedure unless the condition worsened since screening
- A preexisting condition found as a result of screening, unless the condition has worsened since enrollment.

All responses to the above events that require treatment beyond the institution's standard procedures will be reported as AEs.

All procedure AEs and ADEs as described above that are observed during the course of this study, regardless of severity or relationship to the device will be recorded on the appropriate the Club Hernie database tab and on an AE paper form.

The sponsor is responsible for ensuring all Adverse Events reported by the sites are also reported to the EC and to Regulatory Affairs – Medtronic France as required.

### 13.5.1 Adverse Event and Device Deficiency Classification

Causality assessments define the relationship between the use of the medical device (including the medical-surgical procedure) and the occurrence of each adverse event, according to MEDDEV (Guidelines On A Medical Devices Vigilance System). The presence of confounding factors, such as concomitant medication/treatment, the natural history of the underlying disease, other concurrent illness or risk factors shall also be considered. Each AE will be classified according to five different levels of causality. The sponsor and the investigators will use the following definitions to assess the relationship of the serious adverse event to the investigational medical device or procedures:

- Possible Relationship: An AE that follows a reasonable temporal sequence from administration of the study treatment and follows a known response pattern to the study treatment but could have been produced by the participant's clinical state or by other therapies.
- Probable Relationship: An AE that follows a reasonable temporal sequence from administration

of the study treatment; follows a known response pattern to the study treatment; and cannot be reasonably explained by the known characteristics of the participant's clinical state or by other therapies.

- **Causal Relationship:** An AE that follows a plausible temporal sequence from administration of the study treatment and follows a known response pattern to the study treatment. The reaction cannot be reasonably explained by the known characteristics of the subject's clinical state or other modes of therapy administered to the subject.
- **Unknown relationship:** Given the information available, sequence and timing of events, it is unknown or impossible to determine the relationship of the AE with the study treatment.

The Sponsor and the Investigators will distinguish between the serious adverse events related to the device and those related to the index procedures and to mesh placement procedure. An adverse event can be related both to the index and mesh procedures and the device. Complications of procedures are considered not related if the PI said procedures would have been applied to the subjects also in the absence of device use/application.

In some particular cases the event may be not adequately assessed because information is insufficient or contradictory and/or the data cannot be verified or supplemented. The sponsor and the Investigators will make the maximum effort to define and categorize the event and avoid these situations. Where the sponsor remains uncertain about classifying the serious event, it should not exclude the relatedness and classify the event as "possible".

Particular attention shall be given to the causality evaluation of unanticipated serious adverse (device) events. The occurrence of unanticipated events related to the use of the device (USADE) could suggest that the clinical investigation places subjects at increased risk of harm than was to be expected beforehand.

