7.10. Safety Evaluation

Safety evaluation is covered by secondary endpoints.

Listing of AEs, SAEs, ADEs and SADEs, and U(S)ADEs will be provided based on Safety Analysis Set. AEs, SAEs, ADEs and SADEs, and U(S)ADEs will be analyzed using Medical Dictionary for Regulatory Activities (MedDRA v23.1) classification per System Organ Class and Preferred Term and they will also be assessed using the potential risks identified in the Clinical Investigation Plan.

An Adverse Device Effect is an Adverse Event related to device and/or procedure.

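### Requiring a known response pattern for every related causality grade risks under-classifying device effects that are new in nature, and so under-counting ADEs and U(S)ADEs in the SAP listings

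*Protocol*

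**What the plan says.** Protocol section 13.5.1 says that the sponsor and the investigators will use a set of grade definitions "to assess the relationship of the serious adverse event to the investigational medical device or procedures". Three of these assert a relationship, and each includes the pattern condition:

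- Possible: reasonable timing "and follows a known response pattern to the study treatment but could have been produced by" the clinical state or other therapies.
- Probable: the event "follows a known response pattern to the study treatment; and cannot be reasonably explained by the known characteristics" of the clinical state or other therapies.
- Causal: the event "follows a plausible temporal sequence from administration of the study treatment and follows a known response pattern to the study treatment", again with no other reasonable explanation.

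The remaining defined grade, Unknown, applies where "it is unknown or impossible to determine the relationship of the AE with the study treatment".

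Table 4 of the protocol defines a U(S)ADE as a "device effect which by its nature, incidence, severity or outcome has not been identified in the current risk assessment". The same table defines Device Related by whether the event results from the presence or performance of the device, and sets no pattern condition.

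Later in 13.5.1, where the sponsor remains uncertain about classifying a serious event, it is told not to exclude relatedness and to use Possible. The section adds: "Particular attention shall be given to the causality evaluation of unanticipated serious adverse (device) events". It gives no separate criterion for doing so.

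SAP section 7.10 states: "Listing of AEs, SAEs, ADEs and SADEs, and U(S)ADEs will be provided based on Safety Analysis Set". It defines an ADE as an adverse event related to the device and/or procedure.

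**The concern.** The U(S)ADE category exists partly to detect harms nobody foresaw. An effect of a new kind is the one least likely to fit a known pattern, yet the grading rule makes that fit a precondition of calling it related. A new effect with convincing timing and no other explanation could then be left at Unknown because of the wording rather than the evidence.

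The secondary objective is to confirm safety through device- and procedure-related events, so the grade matters for several provisions:

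- **Collection.** Protocol sections 13.1 and 16.1 limit AE collection to device- and procedure-related events.
- **Follow-up.** Section 13.5 extends monitoring beyond study completion, to resolution if possible, only where the investigator determines that the event is related to the device.
- **Reporting.** Table 5 attaches the 7-working-day and 2-day timelines to U(S)ADE status.
- **Analysis.** The ADE, SADE and U(S)ADE listings depend on relatedness.

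Section 14 provides for neither a Data Monitoring Committee nor a Clinical Events Committee, so no independent adjudication is planned that would correct a grade.

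**Working it through.** No sample size, power or rate enters this point. The check is whether the definitions fit together.

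**Step 1. Conditions of each defined grade (protocol 13.5.1).**

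| Grade | Timing | Known pattern | No other reasonable explanation |
|---|---|---|---|
| Possible | required | required | not required |
| Probable | required | required | required |
| Causal | required | required | required |
| Unknown | none | none | none; relationship undetermined |

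The section announces five levels and defines four. No not-related grade is defined.

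**Step 2. Take an effect with no known pattern.** Every row that asserts relatedness fails on the middle condition, so 0 of 3 related grades is open, however good the timing and however well other causes are excluded. Of the defined grades, only Unknown remains.

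**Step 3. Compare with the U(S)ADE definition (Table 4).** It has four alternative routes: nature, incidence, severity and outcome. An infection more severe than the risk assessment foresaw still follows a known pattern and can be graded related. The same holds for unexpected incidence or outcome. Only nature, 1 of the 4 routes, clearly conflicts with step 2.

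**Step 4. Compare with Device Related (Table 4).** An event may result from the presence of the device without matching any known pattern. It is then device-related under Table 4 and meets no related grade under 13.5.1. The protocol does not say which test governs.

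**Step 5. Add the default to Possible (13.5.1, later paragraph).** Four cases with no known pattern:

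1. Serious, and the sponsor remains uncertain: Possible by default. Rescued.
2. Serious, well documented, no other cause, but fitting no known pattern: not clearly rescued. The default sits in a paragraph about insufficient, contradictory or unverifiable information, and here the information is sufficient.
3. Non-serious: not rescued. The default names the serious event only.
4. Not judged related at the site: possibly never reported, so the sponsor may have no occasion to apply the default, which is addressed to the sponsor and not to the investigator.

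**Step 6. Carry through to the SAP.** Section 7.10 does not say which relatedness test feeds its listings. If the 13.5.1 grades do, cases 2 to 4 can be missing from the ADE listing, and the serious ones among them from the SADE and U(S)ADE listings.

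**The case against.** The strongest reply has five parts.

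**The default covers the worst case.** Unknown means that the relationship cannot be determined, which is uncertainty, and for a serious event the sponsor's uncertainty leads to Possible. It is fair to read this as assigning the grade to events that meet no definition, so it does not fail merely because Possible itself mentions the pattern. This stands for case 1 and arguably reaches some of case 2. It does not reach cases 3 and 4.

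**The equation is not in the documents.** Known response pattern is undefined. Nothing says that absence from this device's risk assessment means absence of a known pattern; a response could be known for meshes generally. This stands, and it means that not every effect unanticipated by nature is affected.

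**Nothing says that an Unknown grade removes ADE or U(S)ADE status.** Neither document maps grades to those classes, and Table 4 could be used directly. This stands too, but it leaves two conflicting tests of relatedness with no rule for choosing between them.

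**The grades may apply only to serious events.** The sentence introducing them refers to the serious adverse event. But the same section says that each AE is classified by causality level and offers no other definitions, so non-serious events either fall under these grades or have none.

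**Other safeguards exist.** SAP 7.10 also lists AEs and SAEs and assesses events against the risks named in the protocol. Table 5 sends SAEs to the sponsor within 24 hours, and an internal safety team reviews rates quarterly. These help for events that are reported. Section 13.5, however, lists as reportable the AEs and SAEs that are procedure- or device-related, and its instruction to record regardless of relationship to the device applies to procedure AEs and ADEs. An event judged unrelated at the site can still bypass all of these.

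A reader might infer that no effect of a new kind can ever be graded related, so that the U(S)ADE listing must come out empty for such harms. The first three replies rule that out.

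**Conclusion.** The point holds as an inconsistency that risks under-classification. The pattern condition in 13.5.1 conflicts with the nature route of the U(S)ADE definition and with Device Related in Table 4, and the default to Possible repairs only part of the conflict. The gap is clearest for non-serious effects of a new kind, then for well-documented serious ones, then for events that the site does not judge related.

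The size is structural: 0 of 3 related grades is open on the wording of the grades alone, for 1 of 4 U(S)ADE routes. No expected number of missed events can be given, because the documents state no rate for such effects and any count would also need the strictest reading of the rule. The conclusion assumes that assessors apply the grades as written and that at least some effects new in nature have no known pattern. It does not affect the primary endpoint or its test.

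**What to change.** In protocol 13.5.1, make the known response pattern supporting evidence rather than a required condition of Possible, Probable and Causal; at minimum, remove it as a requirement of Possible. Reconcile the section with Device Related and U(S)ADE in Table 4 so that there is one test of relatedness. Extend the default to Possible to investigators and to non-serious events. In the same edit, bring the number of causality levels announced and the number defined into agreement.

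In SAP 7.10, state that the ADE, SADE and U(S)ADE listings use the reconciled grading.

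The cost is a wording amendment and matching instructions on the AE form. A few more events may be graded related, so the reported ADE figures would look slightly less favourable.

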inclusion and no exclusion criteria, the ICF is signed and they have been implanted with the device. Those subjects who sign the ICF but do not receive ProGrip™ Self-gripping Polyester Mesh will not be included in the study.

- As an on-label Post-Market Clinical Follow-up study to confirm the efficacy and safety of ProGrip™ Self-gripping Polyester Mesh for suture line reinforcement, only device and procedure related AEs will be collected. Non-related AEs (flu, broken limbs, etc.) will not be collected.
- The Club Hernie Data base does not have the capabilities to maintain an audit trail, data trail and edit trail. The sponsor will review all database entries monthly and file securely as an audit trail.

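### Protocol 13.5.1 calls complications of procedures that would have been done without the device not related, without saying to what, so index-procedure events may be classified or reported unevenly

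*Protocol*

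**What the plan says.** **The causality sentence.** Protocol 13.5.1: "Complications of procedures are considered not related if the PI said procedures would have been applied to the subjects" even had the device not been used. The label has no object: not related to the device, or not related to device or procedure.

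**The text around it.** Just before, 13.5.1 requires the sponsor and investigators to "distinguish between the serious adverse events related to the device and those related to the index procedures and to mesh placement procedure", and adds: "An adverse event can be related both to the index and mesh procedures and the device". The section opens by describing causality as the link between an event and use of the device, with the medical-surgical procedure counted as part of that use.

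**The scale.** 13.5.1 announces: "Each AE will be classified according to five different levels of causality". The list that follows has four: possible, probable, causal and unknown.

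**Relatedness classes.** Protocol Table 4 has three: mesh placement procedure, device, and index procedure. The last is defined as "An AE that occurs due to the standard of care index surgical procedure".

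**Collection.** Protocol 16.1: "only device and procedure related AEs will be collected. Non-related AEs (flu, broken limbs, etc.) will not be collected". Protocol 13.1 sets the same scope. Protocol 13.5 makes any procedure- or device-related event reportable. After Table 5 it says "All procedure AEs and ADEs as described above that are observed during the course of this study" are to be recorded whatever their severity or relation to the device.

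**The endpoint.** Adverse event incidence by relationship to procedure and device is a secondary endpoint (Protocol 6.2.2, SAP 7.9) and is analysed descriptively.

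**The concern.** Relatedness does more than sort events here. It decides whether an event enters the data at all, because unrelated events are not collected. A sentence that assigns the not-related label without an object can therefore affect both the classification and the count.

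The events at stake are complications of the laparotomy itself. Protocol 11.7.2 and 11.7.3 name surgical-site infection, hematoma and seroma among the events to collect, so they are of stated interest. Adverse event incidence carries the secondary objective, which is safety. The study has one arm (Protocol 7.2) and no Clinical Events Committee (Protocol 14). Neither a comparator nor independent adjudication would reveal uneven capture between sites. The internal Safety Team in Protocol 14.1 reviews rates quarterly, but it can only review what has been reported.

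**Working it through.** The plan states no figure on this point, so the check is a comparison of texts.

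**Step 1. Which procedures meet the condition?** Inclusion criterion 3 (Protocol 10.3) requires an elective midline laparotomy. That operation is planned whether or not mesh is added, so every index laparotomy meets the condition. Mesh placement does not, since it would not happen without the device. Every enrolled subject has been implanted (Protocol 10.2), so every enrolled subject also has a procedure that the sentence does not cover.

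**Step 2. Not related to what?** Two readings are possible.

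| | A: not related to the device | B: not related at all |
|---|---|---|
| Wording of 13.5.1 | Fits the test of what would have happened without the device | Fits the opening of 13.5.1, which counts the procedure within causality |
| Preceding sentences of 13.5.1 | Consistent | Contradicted |
| Index Procedure Related class, Table 4 | Consistent | Class would have no use |
| Recording instruction in 13.5 | Consistent | Contradicted |

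Reading A is the more coherent. The sentence does not state it.

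**Step 3. What happens to a surgical-site infection attributed to the laparotomy alone?**

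- Under A it is index-procedure related. It is collected under 13.1 and counted in the SAP 7.9 incidence as related to the procedure.
- Under B it is not related. It falls outside the scope in 13.1 and 16.1 and outside the reportable list in 13.5, although 11.7.2, 11.7.3 and the recording instruction in 13.5 still point towards recording it.

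Two sites could each cite the protocol and treat this event differently.

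**Step 4. Can the scale show the difference?** Five levels announced minus four defined leaves one undefined. The label that the sentence assigns is not among the four.

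**Step 5. Adverse device effects.** SAP 7.10 defines these as events related to device and/or procedure. Protocol Table 4 and SAP section 2 define them by use of the device. Even under A, the infection in step 3 is an adverse device effect by SAP 7.10 and not by the other two definitions.

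**Step 6. Size.** The documents give neither an expected rate of procedural events nor the share that sites might leave out. If r is the true proportion of subjects with such an event and s the share left out, reported incidence = r × (1 − s). With assumed values:

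| r | s = 0 | s = 0.25 | s = 0.50 |
|---|---|---|---|
| 10% | 10% | 7.5% | 5% |
| 20% | 20% | 15% | 10% |
| 30% | 30% | 22.5% | 15% |

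This shows how an omission would carry through. It is not evidence that any omission will occur.

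**The case against.** The strongest reply is that the protocol as a whole already settles the matter.

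- The clause about absence of the device suggests attribution to the device, and the preceding sentences make sense only if index-procedure relatedness remains a valid class.
- Table 4 exempts transient nausea and vomiting judged procedure related, and 13.1 waives their reporting. Much of that would be redundant if effects of the index surgery were already outside collection.
- Table 2 schedules adverse event collection at every post-operative visit, and 11.7.2 and 11.7.3 name the wound events.
- The examples of unrelated events in 16.1 are flu and broken limbs, not surgical complications.
- Serious events have further protection: Table 5 requires notification of serious adverse events within 24 hours with no relatedness condition, 13.8 requires all deaths to be reported, and 13.5.1 treats serious events as possibly related where the sponsor is uncertain.
- A wound event in the reinforced incision may be attributed to mesh placement as well, which takes it outside the sentence.

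Most of this stands. It rules out the stronger inference that a reader might draw: that the sentence makes every laparotomy complication unrelated and so removes wound events from the safety data.

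It does not remove the conflict. The wound events in 11.7.2 and 11.7.3 are listed as examples of device effects or procedure-related events, so the relatedness judgement still applies to them. The examples in 16.1 are open-ended. The default to possible covers serious events already known to the sponsor, not non-serious events that a site never sent.

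**Conclusion.** The concern holds as a wording conflict with a possible effect on data capture. Protocol 13.5.1 is ambiguous and, read literally, contradicts Table 4, 13.5 and its own preceding sentences. With collection limited by 13.1 and 16.1, sites could classify or report the same index-procedure complication differently, and some could go unreported. The protocol permits this by poor wording. It does not prescribe it.

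The size cannot be estimated from the documents. A reader might infer that reported incidence could fall to zero. That would need every site to adopt the literal reading, set aside the recording instructions in 11.7.2, 11.7.3 and 13.5, and exclude mesh placement as a contributor every time. The documents do not support that.

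What is exposed is a descriptive secondary endpoint, and through SAP 7.10 the count of adverse device effects. The primary endpoint test is unaffected. The point is worth correcting because the event counts support the safety objective and nothing in the design would show uneven capture.

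**What to change.** 1. In Protocol 13.5.1, limit the sentence to relatedness to the device.
2. State there that complications of the index procedure are still collected and are counted as index-procedure related.
3. Define not related as the fifth causality level, so that an event given that label remains visible.
4. In SAP 7.9 and 7.10, tabulate adverse event incidence separately by relationship to device, mesh placement and index procedure. SAP 7.9 already plans reporting by procedure and device; the addition is the split between the two procedures.
5. Reconcile the definition of an adverse device effect in SAP 7.10 with Protocol Table 4 and SAP section 2.

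The cost is wording in the protocol, the SAP and the adverse event form. No sample size, visit or test changes. The downside for the sponsor is that reported adverse event counts may be less favourable.
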